### 6.2.8 Phone Visit 11 (Maintenance Period Study Day 85)

Site personnel will contact the subject via telephone on Maintenance Period Study Day 85 and record the following:

- AEs
- AESI
- Concomitant Medications

In addition, site personnel with review the diary entries with the parent/caregiver.

# 6.2.9 Clinic Visit 12 (Maintenance Period Study Day 99): End of Study/Early Termination

The End-of-Study participation for an individual subject occurs after he/she has received IMP for 12 weeks in the Maintenance Period. At the End-of-Study visit, the subject may enroll into the separate extension study if they have completed 12 weeks of treatment in the Maintenance Period. Other circumstances for participation in the extension study are described in Section 4.8.

The End-of-Study visit may also occur if the subject withdraws participation from the study or

Confidential Page 57 of 175

the sponsor terminates the study. If the subject withdraws participation from the study, they may on a case-by-case basis, be eligible for entrance into the separate open-label extension study after consideration of the circumstances of the early termination and the potential benefit- risk of continued participation in a ZX008 trial. The decision whether to permit open-label extension study participation resides solely with the sponsor, who may consult with the site investigator. If the sponsor terminates the study early, the subject may or may not be offered enrollment into the open-label extension, depending on the reason for termination.

Subjects will visit the clinic for the End-of-Study visit if one the following events occur:

- 1. The subject withdraws or is withdrawn from participation in the study
- 2. The sponsor terminates the study.
- 3. The subject completes all study related visits and procedures.

### The following procedures will be performed:

- Review current seizure activity (number/type/duration) from diary since previous visit
- Record concomitant medications
- Complete physical examination, including height and weight, and calculation of BMI
- Complete neurological examination
- Obtain vital signs
- 12-lead electrocardiogram
- Doppler ECHO (must be performed any time between Study Day 90 and Study Day 113; if subject terminates early from the study, the ECHO should be scheduled as soon as practical. If the Study Day 43 ECHO was completed ≤30 days prior to early termination, the Visit 12 ECHO will not be performed provided the parent/guardian agrees to bring the subject to the clinic for the cardiac follow-up visit (see Table 7).
- Urine pregnancy test for females of child-bearing potential
- Laboratory evaluation (serum chemistry and hematology, and urinalysis)
- Urine THC panel
- Whole blood CBD
- Collect plasma sample for AED pharmacokinetic evaluation prior to the morning dose of study medication(s)
- Tanner Staging for subjects >7 years of age (Appendix 5)
- Collect and review diary with parent/caregiver
- Dispense diary
- C-SSRS Children's Since Last Visit Assessment (Appendix 2)
- Clinical Global Impression Improvement (assessed by parent/caregiver)
- Clinical Global Impression Improvement (assessed by investigator)
- BRIEF (Appendix 3)
- QOLCE (Appendix 4)
- PedsQL (Appendix 6)

Confidential Page 58 of 175

- PedsQL Family Impact module (Appendix 6)
- Parent/Caregiver QoL using the EQ-5D-5L scale (Appendix 7)
- Affective symptoms of parent/caregiver using the HADS scale (Appendix 8)
- Record AEs
- Record AESIs
- Collect used, partially used and unused study medication; perform drug accountability and review with parent/caregiver
- Dispense study medication for taper for subjects not enrolling in the open-label extension study

Informed consent for the open-label extension study must be signed at Visit 12 (if not signed earlier) in order to enter the open-label extension study.

### 6.3 POST-DOSE VISIT (CLINIC VISIT 13; STUDY DAY 113)

For subjects entering the open-label extension study, the subject will visit the clinic on Study Day 113. The following will be recorded/performed and the subject will immediately be enrolled in that separate study:

- Review current seizure activity (number/type/duration) from diary since previous visit AEs
- AESIs
- Concomitant medications
- Collect used, partially used and unused study medication; perform drug accountability and review with parent/caregiver

If the subject does not enter the open-label extension study (or discontinues from the study early), the subject will visit the clinic on Study Day 113 (or 14 days after the day of discontinuation). The following will be recorded/performed:

- Review current seizure activity (number/type/duration) from diary since previous visit
- AEs
- AESIs
- Concomitant medications
- Collect used, partially used and unused study medication; perform drug accountability and review with parent/caregiver

### 6.4 CARDIAC FOLLOW-UP VISIT (CLINIC VISIT 14; STUDY DAY 197-281)

If the subject completes the study but does not enter the open-label extension study or discontinues from the study early, the subject will return to the clinic for follow-up cardiac testing (ECHO, ECG, and in some cases physical examination). The timing and frequency of exams are in Table 7. Subjects on blinded medication who are found to have been on placebo are not required to participate in follow-up testing once the blind is broken at the end of the study. As

Confidential Page 59 of 175

the ECHO and ECG will be administered in a separate clinic than the pediatric neurology clinic, an asymptomatic subject receiving a second follow-up ECHO and ECG does not require a physical examination.

Subjects with positive findings on ECHO, ECG and/or physical examination should continue to be followed until the finding is resolved or stable and unlikely to change, with reports submitted as AESI to the ZX008 safety database.

Table 7: Schedule of Post-Treatment Cardiac Follow-up

	Duration of Blinded ^a or Fenfluramine Treatment				
Parameter	Less than 2 weeks Cumulative	2 to 4 weeks	>4 and <13 weeks	>13 weeks	Have had any cardiac sign or symptom regardless of the time on study drug ^b
ECHO	No	Yes,	Yes.	Yes,	Yes,
Leno	140	3 months post-	3 months post-	3 and 6 months	3 and 6 months post-
		treatment	treatment	post-treatment	treatment, and until
					resolved, or stable and
					unlikely to change
ECG	No	Yes,	Yes,	Yes,	Yes,
		3 months post-	3 months post-	3 and 6 months	3 and 6 months post-
		treatment	treatment	post-treatment	treatment and until
			79 (0)		resolved, or stable and
		~\ )	0 6		unlikely to change
Physical	No	Yes,	Yes,	Yes,	Yes,
examination		3 months post-	3 months post-	3 months post-	3 and 6 months post-
		treatment	treatment	treatment only	treatment, and until
			2,1		resolved, or stable and
		\ \ \ \ \ \ \ \ \ \ \ \ \ \ \ \ \ \ \			unlikely to change

^a If blind is broken at the end of the study and a subject revealed to have taken only placebo, no further testing is

### 6.5 ESTIMATED BLOOD VOLUME COLLECTION

The maximum total blood volume collected during the study for clinical laboratory testing, genotyping, and PK will be approximately 99.7 mL, as outlined in Table 8.

Confidential Page 60 of 175

Positive sign or symptom includes any development of valve thickening or regurgitation ("trace" or greater in mitral, aortic; mild or greater in pulmonary, tricuspid), or sign or symptom indicative of potential pulmonary hypertension as adjudicated by the IPCAB.

**Table 8:** Estimated Blood Volume Collection*

	Base	line Period (study o	day)	Titration	n + Maintena	nce Period (st	udy day)
Assessment	Screening (Day -42 to -41)	Randomization Day -1	Day 15	Day 43	Day 71	Day 99	Total
Clinical Chemistry	4mL	4mL	4mL	4mL	4mL	4mL	24mL
LH, FSH, Estradiol, Testosterone, Prolactin		4mL		4mL	4mL	4mL	16mL
Genotyping	5 mL		4	2	no diol		5 mL
Hematology	2mL	2mL	2mL	2mL	2mL	2mL	12mL
IGF-1, GH		2.5mL	1166	2.5mL	2.5mL	2.5mL	10 mL
Coagulation		2.7mL	5,510				2.7mL
Cannabidiol	2mL	2mL	2mL	2mL	2mL	2mL	12mL
ZX008 PK plasma	à'Y	oe and		4 x 2 mL			8 mL
AED plasma sample	SULLO	1 x 2 mL	1 x 2 mL	1 x 2 mL		1 x 2 mL	8 mL
Volume for flushing indwelling catheter	Cation			4 x 0.5 mL			2 mL
Approximate total blood volume per subject	13mL	19.2mL	10mL	26.5mL	14.5mL	16.5mL	99.7 mL

FSH=follicle stimulating hormone; GH=growth hormone; IGF-1=insulin-like growth factor 1; LH-luteinizing hormone; PK=pharmacokinetics

Confidential Page 61 of 175

^{*}In concordance with The Seattle Children's Research Foundation Guidance (Appendix 9), blood collection volumes for children weighing up to 15 kg will be:

- the maximum allowable volume of blood in one draw is 22-30 mL (2.5% of total blood volume)
- the maximum in a 30-day period is 44-60 mL.

On Day 43/Visit 8 the pharmacokinetic blood draw will be completed as the priority and the blood draw for chemistry and hematology will be skipped for those subjects who weigh less than 13.5 kg, unless medical concerns (for example, from previous tests or reported side effects) prioritize chemistry and/or hematology.

If blood collection is restricted due to volume or due to inability to draw adequate volume, collection should be prioritized as shown in Table 9:

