### 6.2.5 Clinic Visit 8 (Maintenance Period Study Day 43)

Subjects will report to the clinic in the morning on Maintenance Period Study Day 43. Subjects should not take their morning dose(s) of study medication and AED medication prior to reporting to the clinic. The following procedures will be performed:

- Review current seizure activity (number/type/duration) from diary since previous visit
- Record concomitant medications

Confidential Page 55 of 175

- Abbreviated physical examination, including height and weight, and calculation of BMI (Note: if the subject's weight is ±25% of the weight at Study Day-1, the IMP dose will be recalculated)
- Obtain vital signs
- 12-lead electrocardiogram
- Doppler ECHO (this must be obtained any time between Study Day 40 and Study Day 54)
- Urine pregnancy test for females of child-bearing potential
- Laboratory evaluation (serum chemistry and hematology, and urinalysis)
- Urine THC panel
- Whole blood CBD
- Collect plasma sample for ZX008 pharmacokinetic evaluation at the following timepoints: within 1 hour prior to the morning dose of study medication, and 1, 2 and 4-6 hours after the morning dose of study medication
- Collect plasma sample for AED pharmacokinetic evaluation prior to the morning dose of study medication(s)
- Collect and review diary with parent/caregiver
- Dispense diary
- C-SSRS Children's Since Last Visit Assessment (Appendix 2)
- BRIEF (Appendix 3)
- QOLCE (Appendix 4)
- PedsQL (Appendix 6)
- Affective symptoms of parent/caregiver using the HADS scale (Appendix 8)
- Clinical Global Impression Improvement (assessed by parent/caregiver)
- Clinical Global Impression Improvement (assessed by investigator)
- Record AEs
- Record AESI
- Collect used, partially used and unused study medication; perform drug accountability and review with parent/caregiver
- Dispense study medication

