**Table 9: Priorities for Blood Sample Collections** 

Assessment	0	Priority
ZX008 PK sample		Priority 1
Clinical chemistry		Priority 2
Cannabidiol		Priority 2
AED plasma sample	7, 0	Priority 2
LH, FSH, estradiol, testosterone, GH, prolactin	9 16.	Priority 3
Hematology	5	Priority 3
IGF-1		Priority 4
Genotyping	C VS.	One time collection any time during or after screening
Coagulation	0	One time collection any time before PK day

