## 7.2.5 Laboratory Measurements

Laboratory safety parameters will be analyzed using standard validated methods.

The following parameters will be assessed by the laboratory as described in Table 1:

- Hematology: hemoglobin, hematocrit, erythrocytes, erythrocyte mean corpuscular volume, leukocytes, mean corpuscular hemoglobin, mean corpuscular hemoglobin concentration, neutrophils, lymphocytes, monocytes, eosinophils, basophils and platelets
- Blood Biochemistry: albumin (ALB), alkaline phosphatase (AP), alanine aminotransferase (ALT; SGPT), aspartate aminotransferase (AST; SGOT), bicarbonate, blood urea nitrogen (BUN), calcium (Ca), carbon dioxide (CO₂), chloride (Cl), creatinine, creatine kinase, gamma-glutamyl transferase (GGT), globulin, glucose, lactate dehydrogenase (LDH), phosphorus, potassium (K), sodium (Na), thyroid function (T3, T4, and thyroid stimulating hormone [TSH]),

Confidential Page 66 of 175

total bilirubin, direct bilirubin, total cholesterol, total protein, triglycerides, uric acid.

- Tests of growth and precocious puberty: Growth hormone (GH), insulin-like growth factor-1 (IGF-1, low sensitivity), prolactin, Luteinizing Hormone (LH), Follicle Stimulating Hormone (FSH), testosterone, estradiol
- Epilepsy genotype panel
- Coagulation: Prothrombin time (PT)/International normalized ratio (INR), activated partial thromboplastin time (PTT)
- Whole blood cannabidiol
- Urinalysis: analysis for pH, glucose, ketones, nitrite, protein, bilirubin, urobilinogen, leukocyte esterase, and occult blood. Microscopic analysis will be performed for blood, all cell types, and casts.
- Urine pregnancy test: Urine pregnancy testing will be performed in female subjects of childbearing potential.
- Urine THC panel

The investigator will receive the laboratory report from the central laboratory. After reviewing the report and evaluating any results that are outside the normal range, the investigator must sign and date the laboratory report.

Tests resulting in abnormal laboratory values that have been classified by the investigator as abnormal, clinically significant should be repeated as soon as possible after receiving the laboratory report to rule out laboratory errors.

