### Table 10: Adverse Events of Special Interest (continued)

			
Metabolic/Endocrine			
1.	Elevated prolactin level ≥2x above the upper limit of normal (ULN)		
2.	Galactorrhea		
3.	Gynecomastia		
4.	Increase in fasting serum blood glucose ≥2x ULN		
5.	Hypoglycemia – serum blood glucose more than 20% below the glucose level on Study Day -1 value or more than 10% below LLN (reference range $60-140\mathrm{mg/dL}$ )		
Neuropsychiatric			
1.	Serotonin syndrome (At least 3 of following symptoms must be present: Agitation, restlessness,		
	confusion, both increased HR and blood pressure, dilated pupils, muscle twitching, muscle rigidity,		
	hyperhidrosis, diarrhea, headache, shivering, tremors, both nausea and vomiting)		
2.	Hallucinations		
3.	Psychosis		
4.	Euphoria		
5.	Mood disorders: depression and anxiety if they rise to a level of a disorder		
6.	Suicidal thoughts, ideation or gestures		
Genitourinary			
1.	Priapism		

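### The Table 8 footnote applies Appendix 9's 11-15 kg blood limits to every child up to 15 kg, and the Day 43 low-weight rule drops Priority 2 chemistry where lower-priority tubes could go first

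*Protocol*

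**What the plan says.** Section 6.5 does three things for small children.

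- The footnote to Table 8 cites Appendix 9 and states, for children weighing up to 15 kg, that "the maximum allowable volume of blood in one draw is 22-30 mL (2.5% of total blood volume"), with 44-60 mL in any 30 days.
- On Day 43 (Visit 8) the PK draw comes first, and the draw for "chemistry and hematology will be skipped for those subjects who weigh less than 13.5 kg, unless medical concerns" (such as an earlier result or a reported side effect) give chemistry and/or hematology priority.
- If collection is otherwise restricted, "collection should be prioritized as shown in Table 9". Table 9 puts ZX008 PK at Priority 1; chemistry, cannabidiol and the AED sample at Priority 2; hematology and the group "LH, FSH, estradiol, testosterone, GH, prolactin" at Priority 3; and IGF-1 at Priority 4.

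Appendix 9 assigns 22-30 mL per draw and 44-60 mL per 30 days to the 11-15 kg row. At 10 kg it gives 20 and 40 mL, and at 9 kg 18 and 36 mL.

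The skip rule does not mention the hormone or IGF-1/GH tubes. Section 7.2.5 lists them apart from biochemistry, under "Tests of growth and precocious puberty: Growth hormone (GH), insulin-like growth factor-1" and related tests, and Tables 8 and 9 give them their own rows. The Visit 8 procedure list in Section 6.2.5 names only "Laboratory evaluation (serum chemistry and hematology, and urinalysis").

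**The concern.** The footnote is the only place in Section 6.5 where a volume limit is printed for small children, and it has no lower weight bound. Entry is from age 2 with no minimum weight (Section 4.1), so a child under 11 kg is possible. For such a child the printed 22 mL is above what Appendix 9 allows.

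The skip rule gives up scheduled safety chemistry, which Table 9 ranks just below PK, and leaves the lower-ranked tubes unaddressed. Day 43 is the first scheduled laboratory visit within the Maintenance Period as Section 10.4 defines it. Where no concern is flagged, a child under 13.5 kg has no scheduled chemistry or hematology between Day 15 and Day 71. Chemistry carries glucose, and the hypoglycemia event of special interest in Table 10 is defined partly as "serum blood glucose more than 20% below the glucose level on Study Day -1 value". The override depends on something already known; it does not pick up a silent new abnormality.

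**Working it through.** **Inputs.** Table 8, Day 43 (mL): chemistry 4, hormones 4, hematology 2, IGF-1/GH 2.5, cannabidiol 2, ZX008 PK 4 × 2 = 8, AED 2, catheter flush 4 × 0.5 = 2. Day 71 total: 14.5. Appendix 9: 80 mL/kg above 2 kg, 2.5% per draw, 5% per 30 days.

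**The plan's own figures.** 4 + 4 + 2 + 2.5 + 2 + 8 + 2 + 2 = 26.5 mL, as printed. The limit per draw is 0.025 × 80 = 2 mL/kg, and per 30 days 0.05 × 80 = 4 mL/kg. The full draw therefore needs 26.5 / 2 = 13.25 kg. The 13.5 kg trigger allows 27 mL, a margin of 0.5 mL.

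**What can be kept.** Lowest weight = volume / 2, counting the flush and treating the visit as one draw:

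| Day 43 content | Volume (mL) | Fits from (kg) |
|---|---|---|
| Full | 26.5 | 13.25 |
| Without IGF-1/GH | 24.0 | 12 |
| Also without hormones; chemistry and hematology kept | 20.0 | 10 |
| Also without hematology; chemistry kept | 18.0 | 9 |
| Without IGF-1/GH and hematology; hormones kept | 22.0 | 11 |
| Current rule, hormone and IGF-1/GH tubes stay | 26.5 − 6 = 20.5 | 10.25 |
| Current rule, those tubes also skipped | 26.5 − 12.5 = 14.0 | 7 |

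GH is Priority 3 in Table 9 but shares the IGF-1 tube in Table 8, so the two are dropped together. Without the flush each weight falls by 1 kg.

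**The two readings of the skip.** Read row by row, the hormone and IGF-1/GH tubes stay. Chemistry (Priority 2) is then dropped while Priority 3 and 4 tubes are drawn, and 20.5 mL exceeds the 20 mL limit at 10 kg while passing the footnote's 22 mL. Read through the visit lists, the skip takes the hormone tubes too. Table 9 is then not inverted, but 14.0 mL is drawn where 18 or 20 mL with chemistry would fit.

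**30-day check.** Day 43 and Day 71 are 28 days apart. With chemistry and hematology kept: 20.0 + 14.5 = 34.5 mL, against 40 mL at 10 kg. With chemistry only: 18.0 + 14.5 = 32.5 mL, against 36 mL at 9 kg. The 30-day limit does not bind first.

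**Footnote.** Its lowest figure, 22 mL, exceeds Appendix 9 by 22 − 20 = 2 mL at 10 kg and 22 − 18 = 4 mL at 9 kg.

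**Gap.** 71 − 15 = 56 days.

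**The case against.** The sponsor can say that the rule is explicit, puts PK first and has a medical override. Chemistry is drawn on Days -1, 15, 71 and 99, and the Day 43 urinalysis, ECG and ECHO and the Day 29 and 57 calls remain. All of that stands and keeps the point modest.

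A cut larger than the limit requires also leaves reserve. Section 7.2.5 asks that results judged "abnormal, clinically significant should be repeated as soon as possible", which costs 4 + 2 = 6 mL for chemistry plus hematology, and Section 8.9 asks for a sample after an SAE (4 mL, assuming one 2 mL ZX008 and one 2 mL AED tube). If the skip already covers the hormone tubes, the 30-day reserve at 10.25 kg is 41 − 28.5 = 12.5 mL. Keeping chemistry and hematology leaves 41 − 34.5 = 6.5 mL, which does not cover both needs. This is a real cost on that reading. If the tubes stay, the current reserve is 41 − 35 = 6.0 mL and nothing is lost.

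Four stronger inferences are tempting and not supported:

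- That the whole Day 43 draw fits down to 10 kg. It fits only after 6.5 mL of hormone and IGF-1/GH tubes is removed.
- That Section 6.5 flatly contradicts Table 9. The inversion depends on the row-by-row reading, and Table 9 can be taken to govern whatever restriction is left after the skip.
- That both glucose events of special interest are lost on Day 43. One is defined on fasting glucose, and Visit 8 requires no fasting, so keeping chemistry would not clearly detect it.
- That the footnote leaves sites with no correct limit. It states the right 2.5% and cites Appendix 9.

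**Conclusion.** Two corrections are warranted.

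1. The footnote is wrong below 11 kg: the limits there are 2 mL/kg per draw and 4 mL/kg per 30 days. This holds on the face of Appendix 9.
2. The 13.5 kg trigger is right, but the default removes the wrong sample first and leaves the fate of the hormone and IGF-1/GH tubes unstated. Sites could draw 20.5 or 14.0 mL under the same sentence. Chemistry could be kept from 10 kg with hematology, or from 9 kg without it.

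The weights assume that the flush counts and that the visit is one draw, as the 13.5 kg trigger itself implies. The reach is one visit. The protocol gives no weight distribution, so the number of children affected, and whether any is below 11 kg, is unknown. No efficacy analysis is touched. It should be fixed because it concerns safety limits and costs little; it does not threaten the trial.

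**What to change.** Correct the footnote: 22-30 mL per draw and 44-60 mL per 30 days apply to 11-15 kg; below 11 kg the limits are 2 mL/kg and 4 mL/kg (20 and 40 mL at 10 kg).

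Replace the skip sentence with: *On Day 43, for subjects under 13.5 kg, complete the PK draw first, then omit samples from the lowest Table 9 priority upward (IGF-1/GH, then Priority 3 samples) until the volume is within 2 mL/kg, retaining chemistry where it fits; medical concerns may prioritize any other sample.*

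The sponsor should choose whether hormones or hematology goes first within Priority 3. Fixed weight bands in the laboratory manual would spare sites the calculation but are optional.

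The cost is one sentence and one footnote. Day 43 IGF-1/GH is lost under 13.25 kg, and at lower weights hormones (including prolactin, itself a marker for an event of special interest) or hematology. All are still scheduled on Days -1, 71 and 99. If the current rule already drops the hormone tubes, the smallest children give more blood on Day 43, within Appendix 9, and keep less 30-day reserve.

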**Table 9: Priorities for Blood Sample Collections** 

Assessment	0	Priority
ZX008 PK sample		Priority 1
Clinical chemistry		Priority 2
Cannabidiol		Priority 2
AED plasma sample	7, 0	Priority 2
LH, FSH, estradiol, testosterone, GH, prolactin	9 16.	Priority 3
Hematology	5	Priority 3
IGF-1		Priority 4
Genotyping	C VS.	One time collection any time during or after screening
Coagulation	0	One time collection any time before PK day

# 7. EFFICACY, SAFETY, AND PHARMACOKINETIC ASSESSMENTS

For an overview of the study variables and measurement times, see Schedule of Assessments (Table 1).

Variables used to measure treatment compliance with respect to administration of the IMP are described in Section 5.8.

### 7.1 EFFICACY ASSESSMENTS

Baseline is defined as the seizure frequency during the 6-week Baseline Period.

Retrospective diary data (up to 6 months) will be collected, if available, for an exploratory evaluation of the duration of baseline data capture on interpretation of post-treatment effect.

Confidential Page 62 of 175

For all questionnaires and rating scales, the same evaluator (at the clinical site and parent/caregiver) will complete the assessments for the duration of the study. Substitutions at the clinic with another rater that has established inter-rater reliability is acceptable on an infrequent basis. For the in-clinic questionnaires and rating scales completed by the parent/caregiver, if the same parent/caregiver cannot complete the questionnaire/rating scale at a visit, the questionnaire/rating scale will not be completed. For the diary, the same parent/caregiver will complete all entries throughout the study.

